8.3. Adverse Events of Special Interest Analyses

A comprehensive list of MedDRA terms based on clinical review will be used to identify each type of event. The details of the planned displays are provided in [Appendix 11: List of Data Displays](#).

Adverse Events of Special Interest (AESI) are those AEs associated with the known pharmacological action of ICSs and/or LAMAs and/or LABAs, regardless of whether the AE has been specifically described for FF and/or UMEC and/or VI. AESI groupings are compiled in one of two ways: where SMQs (pre-defined lists of MedDRA PTs) are available from MedDRA for specific AESIs, these are used; and where SMQs are not available, a GSK-defined list of all relevant MedDRA PTs is used.

For FF/UMEC/VI, the special interest groups are: adrenal suppression, corticosteroid-associated and antimuscarinic-associated ocular effects, decreased bone mineral density and associated fractures, hypersensitivity, pneumonia, LRTI excluding pneumonia, local steroid effects, effects on potassium, tremor, CV effects, effects on glucose, asthma/bronchospasm, anticholinergic syndrome. Gastrointestinal obstruction, urinary retention.

[Table 1](#) presents the special interest AE groups for FF, UMEC and VI.

Table 1 AESI definitions

Special Interest AE Group	Special Interest AE Subgroup	PTs for Inclusion
Cardiovascular effects*	Cardiac arrhythmia	Cardiac arrhythmia (SMQ), excluding congenital and neonatal arrhythmias (SMQ)
	Cardiac failure	Cardiac Failure (SMQ)
	Cardiac ischaemia	Ischaemic Heart Disease (SMQ)
	Stroke	Central nervous system haemorrhages and cerebrovascular conditions (SMQ)
	Hypertension	Hypertension (SMQ)
Pneumonia*	Pneumonia	Infective Pneumonia (Narrow SMQ)
LRTI excluding infective pneumonia SMQ*	LRTI excluding infective pneumonia SMQ	Selected PTs

Special Interest AE Group	Special Interest AE Subgroup	PTs for Inclusion
Decreased bone mineral density and associated fractures	Decreased bone mineral density and associated fractures	Osteoporosis/Osteopenia (SMQ) Selected PTs
Hypersensitivity*	Hypersensitivity	Hypersensitivity (SMQ) Angioedema (SMQ) Anaphylactic reaction (SMQ)
Anticholinergic Syndrome*	Anticholinergic syndrome	Anticholinergic Syndrome (SMQ)
Gastrointestinal obstruction*	Gastrointestinal obstruction	Gastrointestinal obstruction (SMQ)
Adrenal Suppression	Adrenal Suppression	Selected PTs
Antimuscarinic ocular effects* / Corticosteroid Associated Eye Disorders	Glaucoma (antimuscarinic / corticosteroid)	Glaucoma (SMQ)
	Cataracts (corticosteroids)	Lens disorders (SMQ)
Effects on Glucose	Effects on Glucose	Hyperglycaemia/new onset diabetes mellitus (SMQ)
Local steroid effects	Local steroid effects	Selected PTs
Urinary retention*	Urinary retention	Selected PTs
Effects on potassium	Effects on potassium	Selected PTs
Tremor	Tremor	Selected PTs
Asthma/Bronchospasm for Asthma-related intubations and deaths	Asthma/Bronchospasm for Asthma-related intubations and deaths	Asthma/bronchospasm (SMQ)
Dry mouth / Drying airway secretions*	Dry mouth / Drying airway secretions	Selected PTs (narrow & broad focus)

*: of interest for UMEC .

Adverse events of special interest will be summarized in the same manner outlined in Section 8.2 for overall AEs.

8.4. MACE

The MACE (Major Adverse Cardiac Events) endpoint will be analyzed using broad and narrow definitions.

The Broad MACE will be defined as follows:

- Cardiac Ischaemia Special Interest AE Subgroup (Ischaemic Heart Disease SMQ) including fatalities,
- Stroke Special Interest AE Subgroup (Central Nervous System Haemorrhages and Cerebrovascular Conditions SMQ) including fatalities

The narrow MACE definition will include only the PTs of “myocardial infarction” and “acute myocardial infarction” in place of the Cardiac Ischaemia Special Interest AE subgroup.

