### 3.3.1. Risk Assessment

Potential Risk of Clinical Significance	Summary of Data/Rationale for Risk	Mitigation Strategy
Investigational Product (IP) [FF/UMEC/VI]		
Cardiovascular effects of UMEC and VI	
UMEC
 
Cardiovascular effects are a potential class effect associated with anti-muscarinic therapies.
 
In the UMEC/VI clinical development program in Chronic Obstructive Pulmonary Disease (COPD) patients, UMEC/VI was generally well tolerated. Overall, a low number of atrial arrhythmias were reported based on 12-lead ECGs, Holter ECGs, or AEs, of which some occurred with a higher incidence in active treatment groups compared to placebo. There was no additive effect with the combination over individual components. Few of these findings were reported as Serious Adverse Events (SAEs) and none were fatal. In a narrow* Major Adverse Cardiac Event (MACE) analysis, the incidence of non-fatal myocardial infarction (Medical Dictionary for Regulatory Activities (MedDRA) Preferred Terms (PTs) of myocardial infarction and acute myocardial infarction) was low (<1%) across all treatment groups, although small imbalances in exposure adjusted frequency were observed between UMEC- and VI containing treatment groups when compared with placebo and tiotropium. There was no obvious dose relationship or additive effect from the combination. Whether this represents a true effect is difficult to determine due to the small numbers. During clinical studies in COPD (62.5 and 125mcg daily dose of UMEC) and in Healthy Volunteers (in the Thorough QT study, UMEC 500mcg daily dose), no effect was observed on heart rate, blood pressure or QT.
 
VI
 
In the FF/VI clinical development program in patients with COPD, the
	
Mitigation strategy for UMEC and VI:
 
 
- Exclusion criteria as specified in Section 6.2. of the protocol
 
- Collection of cardiovascular risk factors and medical history at baseline
 
- ECGs as per schedule in the SoA (Table 1)
 
- Vital sign assessments (blood pressure and pulse rate) as per schedule in the SoA (Table 1)
 
- Cardiovascular AEs and Serious AEs (SAEs) will be captured on the electronic Case Report Form (CRF) (see Section 9.2.5.)
 
- Protocol defined stopping criteria as per Section 8
 
- MACE analysis
 
- Instream review .
 

Potential Risk of Clinical Significance	Summary of Data/Rationale for Risk	Mitigation Strategy

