### 9.2.5. Cardiovascular and Death Events

For any cardiovascular events detailed in [Appendix 3](#) and all deaths, whether or not they are considered SAEs, specific Cardiovascular (CV) and Death sections of the CRF will be required to be completed. These sections include questions regarding cardiovascular (including sudden cardiac death) and non-cardiovascular death.

The CV CRFs are presented as queries in response to reporting of certain CV MedDRA terms. The CV information should be recorded in the specific cardiovascular section of the CRF within one week of receipt of a CV event data query prompting its completion.

The Death CRF is provided immediately after the occurrence or outcome of death is reported. Initial and follow-up reports regarding death must be completed within one week of when the death is reported.

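### Neither MACE definition has a cardiovascular-death component, so a death from arrhythmia or heart failure without an ischaemic or stroke term would be missing from the MACE tables

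*SAP*

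**What the plan says.** SAP 8.4 gives broad MACE two components: "Cardiac Ischaemia Special Interest AE Subgroup (Ischaemic Heart Disease SMQ) including fatalities" and "Stroke Special Interest AE Subgroup (Central Nervous System Haemorrhages and Cerebrovascular Conditions SMQ) including fatalities". For the other version, "The narrow MACE definition will include only the PTs of" myocardial infarction and acute myocardial infarction, and these two terms stand "in place of the Cardiac Ischaemia Special Interest AE subgroup". The stroke component is unchanged. No other component is named.

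Table 1 in SAP 8.3 keeps arrhythmia and heart failure as cardiovascular subgroups of their own. They are defined by "Cardiac arrhythmia (SMQ), excluding congenital and neonatal arrhythmias (SMQ") and "Cardiac Failure (SMQ") respectively, and SAP 8.4 refers to neither.

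Protocol 9.2.5 requires the cardiovascular and death sections of the CRF for every death, regardless of SAE status. On their content it says: "These sections include questions regarding cardiovascular (including sudden cardiac death) and non-cardiovascular death".

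Protocol 3.3.1 lists a MACE analysis among several mitigations for the cardiovascular effects of UMEC and VI, but the protocol does not define MACE for this study.

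**The concern.** A reader of a MACE table expects it to reflect the gravest cardiovascular outcomes. Here, fatal events count only if they fall inside the ischaemia or stroke component. The sponsor asks sites to say whether each death was cardiovascular, yet SAP 8.4 does not use the answer, and no summary table in SAP Appendix 11 is specified to show it.

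The background makes the gap more than formal. On earlier UMEC/VI experience in COPD, Protocol 3.3.1 says: "Overall, a low number of atrial arrhythmias were reported based on 12-lead ECGs, Holter ECGs, or AEs". It adds that some of these were more frequent on active treatment than on placebo, but that few were serious and none fatal.

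At stake is whether the four MACE tables could show zero in a study where a participant died of a cardiovascular cause. Two of them (2.17 and 2.18) belong to the Week 24 summary intended for the Japanese submission.

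**Working it through.** **Step 1: apply the definitions as written.** Inputs are the two definitions in SAP 8.4, the subgroups in SAP Table 1, and the death classification in Protocol 9.2.5. Each row assumes that only the named type of term is coded for the death.

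| Type of death | Broad MACE | Narrow MACE | Could be classified as cardiovascular on the CRF |
|---|---|---|---|
| Myocardial infarction (either of the two preferred terms) | counted | counted | yes |
| Other term in the Ischaemic Heart Disease SMQ | counted | not counted | yes |
| Stroke SMQ term | counted | counted | yes |
| Arrhythmia term only | not counted | not counted | yes |
| Heart-failure term only | not counted | not counted | yes |
| Sudden cardiac death | depends on SMQ contents | not counted unless in the stroke SMQ | yes |

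The arrhythmia and heart-failure rows follow from the subgroups being separate in Table 1. The last row cannot be settled from the documents, because they do not list the preferred terms inside the SMQs. A death that also carries an ischaemic or stroke term would count under the definition that includes that term.

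**Step 2: find where such a death would still be shown.** For a fatal arrhythmia or heart-failure event recorded as an SAE during treatment:

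- Interim: all-AE Table 2.3; SAE Tables 2.11, 2.12 and 2.16; special-interest Tables 2.14 and 2.15; fatal-SAE Listing 18.
- Final: all-AE Table 12.3; SAE Tables 12.23 to 12.26 and 12.34; special-interest Tables 12.30 to 12.33; fatal-SAE Listing 61; patient profiles 93 (arrhythmias), 94 (heart failure) and 101 (all-cause deaths).
- Not shown: MACE Tables 2.17 and 2.18 (interim), 12.36 and 12.37 (final).

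The patient profiles appear only in the final listings; the interim listings have no counterpart.

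**Step 3: size of one uncounted death.** The plan gives no figure to reproduce: neither an expected MACE count nor a cardiovascular death rate. Planned enrolment is 110, with about 100 expected to complete 52 weeks (Protocol 10.1).

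- Proportion, if all 110 are treated: 1/110 = 0.9%.
- Rate, if exposure is 110 person-years (everyone completes): 1000 × 1/110 = 9.1 per 1000 person-years.
- Rate, if exposure is 100 person-years (those who drop out contribute almost nothing): 1000 × 1/100 = 10 per 1000 person-years.

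The exposure range is an assumption. The MACE tables would contribute 0 for this death under both definitions.

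**The case against.** The case for leaving SAP 8.4 alone has several parts.

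- *No rule is broken.* The protocol asks for a MACE analysis without defining it. Its account of an earlier narrow MACE analysis names the same two infarction terms as SAP 8.4, so the definition appears to follow programme practice, and comparability has value. This stands: it is a gap in the SAP, not a contradiction between documents, and the current definitions should be kept.
- *The death would be visible elsewhere.* This also stands. A reader might infer that the death would be hidden in a patient profile, or that its rate would appear as zero throughout the report. The display list does not support that: the SAE and special-interest tables, including the versions per thousand person-years, would show it.
- *No conclusion depends on the MACE count.* A reader might infer that the study's cardiovascular conclusion would be wrong. The documents do not tie any conclusion to MACE. The primary endpoint is the incidence and type of AEs and SAEs, which would capture the death as an SAE. There is no hypothesis test, and MACE is one of several mitigations.
- *The arrhythmia link is indirect.* Protocol 3.3.1 discusses atrial arrhythmias and MACE separately, and arrhythmia has its own special-interest subgroup. So the protocol does not say that MACE is meant to detect arrhythmia.
- *Narrow MACE is meant to be narrow.* A reader might call it an error that narrow MACE drops other fatal ischaemic terms. It is not one: broad MACE picks them up.

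What remains is that the table carrying the MACE label can omit a cardiovascular death for which the CRF already collects the classification.

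**Conclusion.** The point holds as a modest improvement. A death from arrhythmia or heart failure with no ischaemic or stroke preferred term falls outside both definitions and all four MACE tables. For sudden cardiac death the same holds only on the assumption that its term is outside the two SMQs.

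The consequence is an under-inclusive MACE summary that could falsely reassure someone who reads it alone. No data are lost and the primary safety result is unaffected. If one such death occurred, the omission would be 0.9% of 110 participants, or about 9 to 10 per 1000 person-years on the exposure assumed above. The documents give no basis for saying how likely that death is.

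**What to change.** Keep the broad and narrow definitions in SAP 8.4 unchanged and show them as rows, so that comparison with other programme studies is preserved. Add one sentence to 8.4 and two rows to each of Tables 2.17, 2.18, 12.36 and 12.37:

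1. Death classified as cardiovascular on the Death CRF, including sudden cardiac death.
2. MACE (by that table's definition) or cardiovascular death, with each participant counted once. Single counting matters because a fatal infarction, for example, may meet both the MACE definition and row 1.

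The classification is already collected, so no new data are needed. The cost is the sentence, the two rows and the programming behind them, and a total that may be slightly less favourable than the MACE count alone.

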8.5. Clinical Laboratory Analyses

Laboratory evaluations including the analyses of Chemistry laboratory tests, Hematology laboratory tests, Urinalysis, and liver function tests will be based on GSK Core Data Standards. The details of the planned displays are in [Appendix 11: List of Data Displays](#).

Clinical laboratory will be measured at visit 1 (screening visit), 4 (Week 12), 5 (Week 24), 7 (Week 52) or EW. and will be summarized by dose group.

Raw value and change from baseline for laboratory data will be summarized by dose group and total for each visit.

Shifts from baseline relative to the normal range will be also summarized by dose group and total for each visit.

The number of participants with worst case chemistry or hematology will be summarized by test and category. The categories for normal range are: To Low, To Normal or No Change, To High. The categorization is determined by comparing the baseline category to the worst case post-baseline category. The determination of the worst case post-baseline takes into account both planned and unscheduled assessments. The percentages are based on the number of participants in the dose group with data for the test post-baseline. Participants with missing baseline value are to be assumed to have normal/within range baseline value. Note that if a subject has both a decrease ‘To Low’ and an increase ‘To High’, then the subject is counted in both the ‘To Low’ and ‘To High’ categories, so the percentages may not add to 100%.

The number of participants with worst case protein (category: NEG, TRA, 1+, 2+, 3+) or occult blood (category: NEG, TRA, 1+, 2+, 3+) urinalysis results will be summarized by test and category. The categories for worst case are: No Change/Decresed, Any Increase, Increase to TRA, Increase to 1+, Increase to 2+, Increase to 3+. The categorization is determined by comparing the baseline category to the worst case post-baseline category. The determination of the worst case post-baseline takes into account both planned and unscheduled assessments. The percentages are based on the number of participants in the dose group with data for the test post-baseline. Participants with missing baseline value are to be assumed to have normal/within range baseline value.

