#### **Concurrent conditions/medical history**

2. Liver function test at Visit1
  - Alanine aminotransferase (ALT)  $<2 \times$  upper limit of normal (ULN)
  - Alkaline phosphatase  $\leq 1.5 \times$  ULN

- Bilirubin  $\leq 1.5 \times$  ULN (isolated bilirubin  $> 1.5 \times$  ULN is acceptable if bilirubin is fractionated and direct bilirubin  $< 35\%$ )

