11.6. Appendix 6: Derived and Transformed Data

11.6.1. General

Multiple Measurements at One Analysis Time Point

• If there are two values within a time window, the value closest to the target day for that window will be used. If values are the same distance from the target, then the mean will be taken.• Participants having both High and Low values for Normal Ranges at any post-baseline visit for safety parameters will be counted in both the High and Low categories of “Any visit post-baseline” row of related summary tables. This will also be applicable to relevant Potential Clinical Importance summary tables.
Study Day

• Calculated as the number of days from First Dose Date:
• Ref Date = Missing → Study Day = Missing• Ref Date < Treatment Start Date → Study Day = Ref Date – Treatment Start Date• Ref Date ≥ Treatment Start Date → Study Day = Ref Date – (Treatment Start Date) + 1

Example of Handling the Incorrect Treatment and Dose at the Timing of Onset of the AE								
--	--	--	--	--	--	--	--	--

Here are the examples 1- 3 which a given subject had the incorrect treatment in certain period or all periods in treatment period (week 0 to week 52). It is assumed that all participants here complete study (i.e., do not withdraw).

Example	1			2			3		
Dose group	FF/UMEC/VI 100/62.5/25			FF/UMEC/VI 100/62.5/25 to FF/UMEC/VI 200/62.5/25			FF/UMEC/VI 100/62.5/25		
allocated dose at week0	FF/UMEC/VI 100/62.5/25			FF/UMEC/VI 100/62.5/25			FF/UMEC/VI 200/62.5/25		
Switch treatment at week24	No			Yes			No		
Plan dose/ Actual dose/ dose at AE	Plan	Actual	dose at AE	Plan	Actual	dose at AE	Plan	Actual	dose at AE
week0 -4	FF100	FF100	FF100	FF100	FF100	FF100	FF200	FF100	FF100
week4 - 12	FF100	FF100	FF100	FF100	FF200	FF100	FF200	FF100	FF100
week12 - 24	FF100	FF100	FF100	FF100	FF100	FF100	FF200	FF100	FF100
week24 - 36	FF100	FF100	FF100	FF200	FF200	FF200	FF200	FF100	FF100
week36 - 52	FF100	FF200	FF100	FF200	FF100	FF200	FF200	FF100	FF100

Example 1 is the case that a given participant was allocated FF/UMEC/VI 100/62.5/25 at week0 and not switch the study treatment at week24, but had incorrect treatment (i.e., FF/UMEC/VI 200/62.5/25) at week 36 to 52. Therefore, as described in Section 5.1 and Section 8.2, dose group for this participant will be FF/UMEC/VI 100/62.5/25, and AE at week 36 – 52 will be handled as AE at FF/UMEC/VI 100/62.5/25 for dose at AE analyses.

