11.8. Appendix 8: Values of Potential Clinical Importance

This is not applicable to this study.

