No.	Population	IDSL / Example Shell	Title	Programming Notes	Deliverable [Priority]
12.32.	ITT	AE1	Summary of Adverse Events of Special Interest During Treatment Period by dose at AE (dose: FF/UMEC/V1 200/62.5/25)		SAC [1]
12.33.	ITT	Study Specific	Summary of Adverse Events of Special Interest During Treatment Period per Thousand Person-Year by dose group		IA [1]
12.34.	ITT	AE16	Summary of Serious Adverse Events by System Organ Class and Preferred Term during treatment period (Number of Participants and Occurrences)	FDAAA, EudraCT For studies with few events/participants listing is sufficient: discuss this option with your disclosure representative.	SAC [1]
12.35.	ITT	AE3	Summary of Serious Drug-Related Adverse Events by dose group	PLS	SAC [1]
MACE					
12.36.	ITT	Study Specific	Summary of Major Cardiac Events (MACE) – Narrow Definition		SAC [1]
12.37.	ITT	Study Specific	Summary of Major Cardiac Events (MACE) – Broad Definition		SAC [1]
Laboratory: Chemistry					
12.38.	ITT	LB1	Summary of Chemistry Data		SAC [1]
12.39.	ITT	LB1	Summary of Chemistry Changes from Baseline	ICH E3 Includes Baseline values. Includes pre-specified parameters repeated in conventional units.	SAC [1]
12.40.	ITT	LB3	Summary of Chemistry Shifts from Baseline Relative to Normal Range		SAC [1]

CONFIDENTIAL

207236

Safety: Tables					
No.	Population	IDSL / Example Shell	Title	Programming Notes	Deliverable [Priority]
Laboratory: Hematology					
12.41.	ITT	LB1	Summary of Hematology Data		SAC [1]
12.42.	ITT	LB1	Summary of Hematology Changes from Baseline	ICH E3 Includes baseline values.	SAC [1]
12.43.	ITT	LB3	Summary of Hematology Shifts from Baseline Relative to Normal Range		SAC [1]
Laboratory: Urinalysis					
12.44.	ITT	UR1	Summary of Worst Case Urinalysis Results (Discrete or Character Values) Post-Baseline Relative to Baseline	ICH E3 As above for Chemistry, using dipstick categories. Define change categories according to actual values expected from lab dataset	SAC [1]
Vital Signs					
12.45.	ITT	VS1	Summary of Vital Signs	ICH E3 Includes Baseline values.	SAC [1]
12.46.	ITT	VS1	Summary of Change from Baseline in Vital Signs	ICH E3 Includes Baseline values.	SAC [1]
ECG					
12.47.	ITT	EG2	Summary of ECG Values	IDSL	SAC [1]
12.48.	ITT	EG2	Summary of Change from Baseline in ECG Values	IDSL	SAC [1]
12.49.	ITT	Study Specific	Summary of Categories for QTc (F) Values (Interim)	IDSL	SAC [1]

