No.	Population	IDS / Example Shell	Title	Programming Notes	Deliverable [Priority]
62.	ITT	AE8	Listing of Non-Fatal Serious Adverse Events	ICH E3 Fatal and Non-Fatal SAEs are combined into a single listing for ClinPharm studies (i.e., "Listing of Serious Adverse Events").	SAC [1]
63.	ITT	AE14	Listing of Reasons for Considering as a Serious Adverse Event	ICH E3	SAC [1]
64.	ITT	AE8	Listing of Adverse Events Leading to Withdrawal from Study / Permanent Discontinuation of Study Treatment	ICH E3	SAC [1]
65.	ITT	AE8	Listing of Adverse Events of Special Interest	ICH E3 Required for studies where interventions other than withdrawal from treatment or study are possible.	SAC [1]
Hepatobiliary (Liver)					
66.	ITT	MH2	Listing of Medical Conditions for Participants with Liver Stopping Events	IDS	SAC [1]
67.	ITT	SU2	Listing of Substance Use for Participants with Liver Stopping Events	IDS	SAC [1]
68.	ITT	LIVER5	Listing of Liver Monitoring/Stopping Event Reporting	IDS	SAC [1]

CONFIDENTIAL

207236

ICH: Listings					
No.	Population	IDSL / Example Shell	Title	Programming Notes	Deliverable [Priority]
All Laboratory					
69.	ITT	LB5	Listing of Chemistry Values for Subjects with Any Value Outside Normal Range	ICH E3 May be split into separate listings by chemistry, hematology, etc. Display ALL labs for a subject who experienced a value of potential clinical importance.	SAC [1]
70.	ITT	LB5	Listing of Haematology Values for Subjects with Any Value Outside Normal Range	ICH E3 May be split into separate listings by chemistry, hematology, etc. Display ALL labs for a subject who experienced a value of potential clinical importance.	SAC [1]
71.	ITT	UR2A	Listing of Urinalysis Data (Protein and Occult Blood)	Protein and occult blood only. All subjects data need to be displayed.	SAC [1]
ECG					
72.	ITT	EG3 (modified)	Listing of ECG Values for Subjects with any Abnormal ECG Finding	IDSL Required for ClinPharm studies only.	SAC [1]
73.	ITT	EG5	Listing of Abnormal ECG Findings	IDSL Required for ClinPharm studies only.	SAC [1]

CONFIDENTIAL

207236

ICH: Listings					
No.	Population	IDSL / Example Shell	Title	Programming Notes	Deliverable [Priority]
Vital Signs					
74.	ITT	VS4	Listing of Vital Signs	IDSL Required for ClinPharm studies only.	SAC [1]

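### The chemistry and haematology shift rule counts further worsening from an abnormal baseline as no change, and no other laboratory table counts those participants

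*SAP*

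**What the plan says.** Clinical laboratory tests are a secondary safety endpoint (SAP 2.2). For chemistry and haematology, SAP 8.5 plans three things.

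- **Values and changes by visit:** "Raw value and change from baseline for laboratory data will be summarized by dose group and total for each visit".
- **Shifts by visit** relative to the normal range.
- **A worst-case shift summary:** "The categories for normal range are: To Low, To Normal or No Change, To High". The assignment rule is: "The categorization is determined by comparing the baseline category to the worst case post-baseline category". Planned and unscheduled assessments both count towards the worst case.

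SAP Appendix 8, on values of potential clinical importance, says only: "This is not applicable to this study". Two other places still assume such values exist. SAP 11.6.1 gives a rule for participants with both High and Low values and adds: "This will also be applicable to relevant Potential Clinical Importance summary tables". The programming notes to Listings 26 and 27 (interim) and 69 and 70 (final) say: "Display ALL labs for a subject who experienced a value of potential clinical importance".

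The Protocol admits participants with some raised liver tests. Under "Liver function test at Visit1", the Visit 2 inclusion criteria allow ALT below 2 times ULN, alkaline phosphatase and bilirubin up to 1.5 times ULN, and isolated bilirubin above that if the direct fraction is below 35%.

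**The concern.** The shift rule looks only at which side of the normal range a value lies, not how far outside it is. Participants who start outside the range can worsen by any amount in the same direction and still be counted as unchanged. They are also pooled with participants who improved, so the middle category cannot be read as reassurance.

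A clinical-importance table would normally fill this gap, but Appendix 8 removes it and SAP Appendix 11 lists no other threshold or graded table for chemistry or haematology. In a single-arm safety study, where the laboratory evidence is a set of descriptive counts, that leaves a secondary endpoint without an objective count of marked worsening in people who entered with abnormal values.

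**Working it through.** The plan states no figure to reproduce. The check applies the classification rule to test values and then follows each laboratory value to the displays that can contain it.

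**Step 1. The rule applied.** The category depends on the baseline range category and the worst post-baseline range category. Values are illustrative, in multiples of ULN, with High meaning above 1.0. Fold change = worst / baseline.

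| Baseline | Worst | Fold change | Shift category |
|---|---|---|---|
| 0.9 | 1.01 | 1.01/0.9 = 1.1 | To High |
| 1.1 | 7.9 | 7.9/1.1 = 7.2 | To Normal or No Change |
| 1.9 | 7.9 | 7.9/1.9 = 4.2 | To Normal or No Change |
| 1.9 | 0.5 | 0.5/1.9 = 0.26 | To Normal or No Change |

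A trivial crossing of the limit is flagged. A 4-fold or 7-fold rise from an abnormal start shares a cell with recovery. By symmetry, a Low value that falls further is treated the same way.

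**Step 2. How large a hidden ALT rise can be.** An eligible participant who is High for ALT at screening lies between 1 and 2 times ULN. Reaching the multiples in Protocol Appendix 6 from there needs at least these rises:

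- 3 times ULN: from 3/2 = 1.5-fold to 3/1 = 3-fold
- 5 times ULN: from 5/2 = 2.5-fold to 5/1 = 5-fold
- 8 times ULN: from 8/2 = 4-fold to 8/1 = 8-fold

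All are High to High, so all are counted as no change.

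**Step 3. Where such a value can appear.**

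- *By-visit value and change tables* (final Tables 12.38, 12.39, 12.41, 12.42). Table 12.39, "Summary of Chemistry Changes from Baseline", carries the size of change at group level. SAP 11.5.2 defines the statistics only by reference to a sponsor standard, so the documents do not say whether minimum and maximum are shown.
- *Shift tables* (12.40, 12.43). They use range categories only.
- *Threshold or graded tables.* None is listed for chemistry or haematology, at interim or final.
- *Listings.* Listings 69 and 70 cover anyone with any out-of-range value. Listings 66 to 68 and 89 to 92 cover liver events.

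**Step 4. Unscheduled and withdrawal values.** SAP 11.5.2 keeps unscheduled visits out of summary tables except in a worst-case assessment. SAP 11.7.1 says withdrawal visits are neither slotted nor summarised as a visit. I read the withdrawal visit as a planned assessment for the worst-case rule, since it is in the schedule of activities. SAP 8.6.2 names it explicitly for ECG, but 8.5 does not. On that reading, the only chemistry or haematology table that takes in these values is the worst-case shift summary, where High to High is no change. This matters because Protocol 8.1.3 withdraws anyone who stops treatment, and Protocol Appendix 6 calls for repeat liver tests within days or weekly, outside the visit schedule.

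**Step 5. Comparison within the SAP.** Worst-case urinalysis for protein and occult blood is graded up to 3+ (SAP 8.5). QTcF is categorised by value and by change, including the post-baseline maximum (SAP 8.6.2). Chemistry and haematology have neither.

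**The case against.** A reader might infer that no table shows marked worsening at all. The documents do not support that. The change-from-baseline tables carry its size at group level, and may show extremes if the sponsor's standard includes them. Urinalysis is graded. Protocol 9.4.4 requires clinically relevant laboratory changes to be recorded as adverse events, so they can reach the AE tables. Effects on glucose and on potassium are special-interest groups with their own tabulation (SAP 8.3).

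A severe liver case is also unlikely to be overlooked. ALT at or above 8 times ULN triggers discontinuation, a report within 24 hours and a liver-event form, and possible Hy's Law cases must be reported as SAEs.

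Nor do the documents support saying that participants drop out of the listings. Listings 26, 27, 69 and 70 are defined by title for any out-of-range value, so anyone High at baseline qualifies. The note about clinical importance may be leftover template text, and the mention in 11.6.1 has no planned table to act on.

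Finally, this is a descriptive study of 110 participants with no hypotheses, and not setting clinical-importance limits can be defended.

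Most of this stands, and it limits the point. Two things remain. The AE route depends on investigator judgement, and Protocol Appendix 3 excludes abnormal findings tied to underlying disease unless they are more severe than expected. And neither listings, group means nor event reports give a rule-based count of participants who worsened markedly from an abnormal baseline.

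**Conclusion.** The point holds in a limited form. Under SAP 8.5, a chemistry or haematology value already outside the range that worsens in the same direction is tabulated with participants who normalised. With Appendix 8 empty, no chemistry or haematology table counts marked worsening from an abnormal baseline. The information is dispersed across group-level change summaries, listings and AE or liver-event reports, not lost. The gap is sharpest for unscheduled and early-withdrawal values.

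For an eligible ALT, a rise of 4-fold to 8-fold, enough to reach 8 times ULN, is recorded in the shift table as no change. The number of participants affected cannot be given: the documents state neither how many start outside the range nor how many of those worsen, and a count of the first would not measure the second.

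The conclusion assumes that the sponsor's unseen display standards add no threshold table, since none appears in SAP Appendix 11. The references to clinical-importance values in 11.6.1 and the listing notes conflict with Appendix 8 in any case. Overall this is a worthwhile, inexpensive improvement and does not invalidate the safety analysis.

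**What to change.** 1. In the worst-case shift table, report normalisation and no change separately, or show the full cross-tabulation of baseline category by worst category. This removes the pooling but still cannot show size within High or Low, hence item 2.
2. Add one worst-case post-baseline liver table, at interim and final, crossed with baseline category and explicitly including unscheduled and withdrawal values. As reporting categories only, use the ALT multiples in Protocol Appendix 6 (at least 3, 5 and 8 times ULN) and its combined criterion of ALT at least 3 times ULN with bilirubin at least 2 times ULN, keeping the qualifier of more than 35% direct bilirubin. Bilirubin at 2 times ULN alone is not a stopping criterion there and should not be presented as one. The sponsor should decide whether to set limits for other analytes such as glucose and potassium.
3. Reconcile SAP 11.6.1 and the notes to Listings 26, 27, 69 and 70 with Appendix 8, by defining the values or deleting the references.

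The cost is SAP wording and one extra table per delivery. ALT and total and direct bilirubin are already collected (Protocol Table 8). No new data and no change to patient management are involved.
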